6.3.2. Main Analyses of Key Secondary Efficacy Endpoints

6.3.2.1. Monocular Maximum Reading Speed

Maximum reading speed will be calculated per MNRead or Radner user manuals, with no adjustment for reading inaccuracy. An additional step to cap resulting reading speed values at a maximum of 300 words per minute will be implemented. Values above 300 words per minute exceed values reported in the literature for adults with no vision impairment for MNRead (Calabrese et al. 2016) or Radner (Radner et al. 2002; Radner and Diendorfer 2014) assessments. Maximum reading speed will be calculated as the mean of the three highest nonzero reading speeds (or two, or one value, as available) (Baskaran et al. 2019; Patel et al. 2011), except when all words per minute are calculated as 0: then the maximum reading speed will be calculated as 0.

Monocular maximum reading speed in the study eye will be summarized and analyzed in a similar fashion as the primary efficacy endpoint using MMRM described in Section 6.2.2. The model will include treatment (PM, PEOM, Sham), presence of CNV in the fellow eye (yes or no), and baseline GA lesion area ($< 7.5 \text{ mm}^2$ or $\geq 7.5 \text{ mm}^2$) as fixed effects; baseline monocular maximum reading speed as well as the chart type (MNRead or Radner) as covariates, time (in months) as a factor; the time \times treatment interaction term as well as the baseline monocular maximum reading speed \times time interaction term.

The observed values for the monocular maximum reading speed will be summarized by treatment group and visit for both the study and the fellow eye. Summaries will present the descriptive statistics for baseline, absolute values and change from baseline data.

The mean change from baseline in the monocular maximum reading speed of the study eye \pm the standard error as well as the LS mean of the change from baseline in the monocular maximum reading speed of the study eye \pm the standard error will be plotted over time by treatment group.

In addition, the categorical changes (improvements of ≥ 20 to <40 , ≥ 40 to <60 , ≥ 60 and minimal/no change (-20 to 20), worsening of ≥ 20 to <40 , ≥ 40 to <60 , ≥ 60) for the study eye will be summarized by treatment group and visit.

The shift from baseline in the monocular maximum reading speed for the study eye categories over time will be presented by treatment group for the following categories:

- < 40 wpm
- 40 to < 80 wpm
- 80 to <160 wpm
- ≥ 160 wpm

All monocular maximum reading speed data will be listed for the ITT set.

6.3.2.2. Mean FRI Index Score

The mean FRI Index score will be calculated per the scoring algorithm in the FRI Index user's manual.

The mean FRI Index score will be summarized and analyzed in a similar fashion as the primary efficacy endpoint using MMRM described in Section 6.2.2. The model will include treatment

(PM, PEOM, Sham), presence of CNV in the fellow eye (yes or no), and baseline GA lesion area ($< 7.5 \text{ mm}^2$ or $\geq 7.5 \text{ mm}^2$) as fixed effects; baseline mean FRI Index score and baseline study eye status (Better-seeing Eye vs. Worse-seeing Eye) as covariates, time (in months) as a factor; the time \times treatment interaction term as well as the baseline mean FRI Index score \times time interaction term.

The observed values for the mean FRI Index score will be summarized by treatment group and visit. Summaries will present the descriptive statistics for baseline, absolute values and change from baseline data.

The mean change from baseline in the mean FRI Index score \pm the standard error as well as the LS mean of the change from baseline in the mean FRI Index score \pm the standard error will be plotted over time by treatment group.

In addition, the mean FRI Index score will be converted to the FRI Level variable, as per the user manual, ranging from 1 (Unable to do) to 4 (Totally independent). The categorical changes from baseline (improvements (an increase in FRI level), minimal/no change (no change in FRI level), and worsening (decrease in FRI level)) will be summarized by treatment group and visit. The shift from baseline in the FRI level over time will be presented by treatment group.

All FRI data will be listed for the ITT set.

6.3.2.3. NL-BCVA Score

The mean NL-BCVA score for the study eye will be summarized and analyzed in a similar fashion as the primary efficacy endpoint using MMRM described in Section 6.2.2. The model will include treatment (PM, PEOM, Sham), presence of CNV in the fellow eye (yes or no), and baseline GA lesion area ($< 7.5 \text{ mm}^2$ or $\geq 7.5 \text{ mm}^2$) as fixed effects; baseline NL-BCVA score as a covariate, time (in months) as a factor; the time \times treatment interaction term as well as the baseline NL-BCVA score \times time interaction term. Note, for the second year, only timepoints that were measured for all three treatment groups will be included in the model.

The observed values for the NL-BCVA will be summarized by treatment group and visit for both the study and the fellow eye. Summaries will present the descriptive statistics for baseline, absolute values and change from baseline data.

The mean change from baseline in the NL-BCVA score for the study eye \pm the standard error as well as the LS mean of the change from baseline in the NL-BCVA score for the study eye \pm the standard error will be plotted over time by treatment group.

In addition, the categorical changes (improvements of ≥ 15 , ≥ 10 to < 15 , ≥ 5 to < 10 , and minimal/no change (-4 to 4), worsening of ≥ 5 to < 10 , and ≥ 10 to < 15 and ≥ 15) for the study eye will be summarized by treatment group and visit.

The shift from baseline in the NL-BCVA of the study eye categories (≥ 70 , $\geq 60 - < 70$, $\geq 35 - < 60$, $\geq 20 - < 35$, < 20 ETDRS letters over time will be presented by treatment group and visit. The above-mentioned ETDRS letter thresholds are based on WHO definitions for vision impairment and blindness. WHO criteria were implemented in an attempt to capture the progressive nature of

Geographic Atrophy and the ultimate treatment goal of avoiding successive vision impairment and blindness through application of active treatment (Pegcetacoplan vs. Sham).^[1]

The average NL-BCVA score over the last 3 months for each reporting period (Month 10 - Month 12 for the Month 12 reporting; Month 22 - Month 24 for the Month 24 reporting) will be calculated for each subject who has at least one NL-BCVA assessment in these windows. The observed values for the NL-BCVA and changes from baseline will be summarized by treatment group for the study eye. Summaries will present the descriptive statistics for baseline, absolute values and change from baseline data.

All NL-BCVA data will be listed for the ITT set.

6.3.3. Sensitivity Analyses of Key Secondary Efficacy Endpoints

The missing data analyses based on imputation described in Section 6.2.3.1 will be repeated for the key secondary efficacy endpoints at the time of the final study analysis for the full 24 months only. The key secondary endpoints will also be analyzed without pooling the two sham arms (SM and SEOM) for the full 24 months only.

In addition, to assess the potential effect of different assessment tools, the main analysis of monocular maximum reading speed will be repeated by reading chart type. Maximum reading speed with adjustment for reading inaccuracy will also be analyzed, only in the study eye, for the first 12 months as well as the full 24 months.

6.3.4. Supplementary Analyses of Key Secondary Efficacy Endpoints

The supplementary analyses described for the primary endpoint in Section 6.2.4.1 and Section 6.2.4.2 will also be performed for the key secondary endpoints for the first 12 months as well as the full 24 months.

6.3.5. Subgroup Analyses of Key Secondary Efficacy Endpoints

The subgroup analyses of the key secondary endpoints will be performed for the full 24 months. Select subgroup analyses of the key secondary endpoints may be performed at Month 12, if necessary, to support regulatory filings. The subgroups evaluated for key secondary endpoints will be the same as evaluated for the primary efficacy endpoint (see Section 6.2.5).

In addition, the following subgroup analyses will be performed:

Monocular Maximum Reading Speed

- Study eye baseline monocular maximum reading speed (<60, 60-<160, ≥160 wpm)

Mean FRI Index score

- Baseline Study Eye Status (Better-seeing Eye vs. Worse-seeing Eye)

For each endpoint, a MMRM similar to that specified for the main analysis of the key secondary endpoints (Section 6.3.2) will be used for each subgroup analysis based on the data subset for the subject subgroup of interest. Baseline covariates included in the main analysis but no longer

^[1] approximated from 6/18; see <https://icd.who.int/browse11/1-m/en#/http://id.who.int/icd/entity/1103667651>

relevant given the subgroup of interest will be excluded from the model. The estimated treatment effects (PM vs. Sham or PEOM vs. Sham) and corresponding 95% CIs and p-values from the models will be displayed graphically for each pegcetacoplan arm and each level of the subgroups specified (e.g., via forest plots).

6.4. Analyses of Other Secondary Efficacy Endpoints

The secondary efficacy endpoints are listed in Section 2.2.3. At the time of the Month 12 reporting, all secondary efficacy endpoints will be evaluated based on data from baseline to Month 12 (see Section 3.5). For the Month 12 analyses, post-baseline visits, up to and including Month 12, will be included. At the time of the final study analysis, all secondary efficacy endpoints will be evaluated based on data from baseline to Month 24. For the Month 24 analyses, post-baseline visits, up to and including Month 24, will be included.

Unless otherwise specified, all secondary efficacy endpoints will be analyzed for the mITT set.

6.4.1. Low Luminance Best-Corrected Visual Acuity (LL-BCVA)

LL-BCVA of the study eye will be summarized and analyzed in the similar fashion as the primary efficacy endpoint using MMRM described in Section 6.2.2. The model will include treatment (PM, PEOM, Sham), presence of CNV in the fellow eye (yes or no), and baseline GA lesion area ($< 7.5 \text{ mm}^2$ or $\geq 7.5 \text{ mm}^2$) as fixed effects; baseline LL-BCVA score as a covariate, time (in months) as a factor; the time \times treatment interaction term as well as the baseline LL-BCVA score \times time interaction term. Note, for the second year, only timepoints that were measured for all three treatment groups will be included in the model.

The observed values for the LL-BCVA will be summarized by treatment group and visit for both the study and the fellow eye. Summaries will present the descriptive statistics for baseline, absolute values and change from baseline data.

The mean change from baseline in the LL-BCVA score in the study eye \pm the standard error as well as the LS mean of the change from baseline in the LL-BCVA score in the study eye \pm the standard error will be plotted over time by treatment group.

The categorical changes (improvements of ≥ 15 , ≥ 10 to < 15 , ≥ 5 to < 10 , and minimal/no change (-4 to 4), worsening of ≥ 5 to < 10 , and ≥ 10 to < 15 and ≥ 15) for the study eye will be summarized by treatment group and visit.

Additionally, the average LL-BCVA score over the last 3 months for each reporting period (Month 10 - Month 12 for the Month 12 reporting; Month 22 - Month 24 for the Month 24 reporting) will be calculated for each subject who has at least one LL-BCVA assessment in these windows. The observed values for the LL-BCVA and changes from baseline will be summarized by treatment group for the study eye. Summaries will present the descriptive statistics for baseline, absolute values and change from baseline data.

The same subgroup analyses as described for NL-BCVA in Section 6.3.5 will also be repeated for LL-BCVA for the full 24 months.

All LL-BCVA data will be listed for the ITT set. In addition, the low luminance deficit will be calculated as the difference between NL-BCVA and LL-BCVA and listed for the ITT set.

6.4.2. Total Area of GA lesion(s) at Each Planned Assessment

The change from baseline at each planned assessment (other than Month 12 and Month 24) in the total area of GA lesion(s) in the study eye, as assessed by FAF, will be estimated from the MMRM analyses described in Section 6.2.2.

6.4.3. Monocular Critical Print Size

Critical print size will be calculated as the smallest print size which support reading speed at 80% of the maximum reading speed, without adjustment for reading inaccuracy (Baskaran et al. 2019).

Monocular critical print size of the study eye will be summarized and analyzed in a similar fashion as the primary efficacy endpoint using MMRM described in Section 6.2.2. The model will include treatment (PM, PEOM, Sham), presence of CNV in the fellow eye (yes or no), and baseline GA lesion area ($< 7.5 \text{ mm}^2$ or $\geq 7.5 \text{ mm}^2$) as fixed effects; baseline monocular critical print size as well as the chart type (MNRead or Radner) as covariates, time (in months) as a factor; the time \times treatment interaction term as well as the baseline monocular critical print size \times time interaction term.

The observed values for the monocular critical print size will be summarized by treatment group and visit for both the study and the fellow eye. Summaries will present the descriptive statistics for baseline, absolute values and change from baseline data.

To assess the potential effect of different assessment tools, the analysis of monocular critical print size will be repeated by chart type.

All monocular critical print size data will be listed for the ITT set.

6.4.4. NEI VFQ-25 Distance Activity Subscale Score

NEI VFQ-25 distance activity subscale score will be calculated per the scoring algorithms in user's manual.

NEI VFQ-25 distance activity subscale score will be summarized and analyzed in a similar fashion as the primary efficacy endpoint using MMRM described in Section 6.2.2. The model will include treatment (PM, PEOM, Sham), presence of CNV in the fellow eye (yes or no), and baseline GA lesion area ($< 7.5 \text{ mm}^2$ or $\geq 7.5 \text{ mm}^2$) as fixed effects; baseline NEI VFQ-25 distance activity subscale score and baseline study eye status (Better-seeing Eye vs. Worse-seeing Eye) as covariates, time (in months) as a factor; as well as the time \times treatment interaction term as well as the baseline NEI VFQ-25 distance activity subscale score \times time interaction term.

The observed values for the NEI VFQ-25 distance activity subscale score will be summarized by treatment group and visit. Summaries will present the descriptive statistics for baseline, absolute values and change from baseline data.

The categorical changes (improvements of >5 units and minimal/no change (-5 to 5), worsening of a decrease of >5 units) will be summarized by treatment group and visit.

In addition, the shift from baseline in NEI VFQ-25 distance activity subscale score categories (>80 , $>65 - \leq 80$, $>50 - \leq 65$, $\geq 35 - \leq 50$, <35) will be summarized by treatment group and visit.

All NEI VFQ-25 data will be listed for the ITT set.

6.5. Multiplicity Adjustment

No hypothesis testing of the (non-key) secondary endpoints will be performed. Control of Type I error for (non-key) secondary endpoints is not applicable.

6.6. Analyses of Exploratory Endpoints

The exploratory efficacy endpoints are listed in Section 2.2.4. At the time of Month 12 reporting, all exploratory efficacy endpoints will be evaluated based on data from baseline to Month 12 (see Section 3.5). For the Month 12 analyses, post-baseline visits, up to and including Month 12, will be included. At the time of the final study analysis, all exploratory efficacy endpoints will be evaluated based on data from baseline to Month 24. For the Month 24 analyses, post-baseline visits, up to and including Month 24, will be included.

Unless otherwise specified, all exploratory efficacy endpoints will be analyzed for the mITT set.

6.6.1. NEI VFQ-25 and NEI VFQ-39 Additional Analyses

Descriptive summary statistics for baseline, absolute values and change from baseline data will be provided by treatment group and visit for the following NEI VFQ-25 and NEI VFQ-39 scores:

- NEI VFQ-39 distance activity subscale
- NEI VFQ-25 composite score
- NEI VFQ-39 composite score
- NEI VFQ-25 near activity subscale score
- NEI VFQ-39 near activity subscale score
- NEI VFQ-25 driving subscale score (for subjects who are currently driving at baseline)

The shift from baseline in NEI VFQ score categories (>80 , $>65 - \leq 80$, $>50 - \leq 65$, $\geq 35 - \leq 50$, <35) will be summarized by treatment group and visit for the scores described above.

In addition, the categorical changes (improvements of >5 units and minimal/no change (-5 to 5), worsening of a decrease of >5 units) will be summarized by treatment group and visit for the following NEI VFQ-25 Scores: Composite and Near Activity.

For the NEI VFQ-25 Driving subscale score, the number and percentage of subjects with a worsening driving outcome compared to baseline will be summarized by treatment group and visit. Each visit will display the number of patients who were driving at baseline with at least one of the worsening driving outcomes. The categories to determine worsening driving outcomes are: conversion to no longer currently driving, increase in difficulty driving in familiar places in daytime, increase in difficult driving at night or stopped doing this due to vision, increase in difficulty driving in difficult conditions or stopped doing this due to vision.

All NEI VFQ-25 data will be listed for the ITT set.

6.6.2. Binocular Maximum Reading Speed and Critical Print Size

Descriptive summary statistics for baseline, absolute values and change from baseline data will be provided by treatment group and visit for the binocular maximum reading speed and critical print size with no adjustment for reading inaccuracy. All binocular maximum reading speed and critical print size data will be listed for the ITT set.

Categorical changes over time and categorical shifts from baseline will be presented, as will be done for the monocular reading speed.

6.6.3. GA Lesion (s) Study Eye to Fellow Eye Comparisons

Descriptive summary statistics will be provided by treatment and visit for the change from baseline in total area of GA Lesion(s) for the study eye as well as for the fellow eye in subjects with bilateral GA with fellow eyes that satisfy the following characteristics at baseline:

- Absence of CNV in the medical history
- Baseline GA lesion size between 2.5 and 17.5 mm²
- Presence of any pattern of hyperautofluorescence in the junctional zone of GA
- GA not confluent with any peripapillary atrophy

The change from baseline in total area of GA Lesion(s) \pm the standard error in the study eye as well as the fellow eye will be plotted over time by treatment group for the subjects with bilateral GA with fellow eyes that satisfy the above characteristics.

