### 5.1.5. Exploratory Objectives

- To evaluate the efficacy of pegcetacoplan compared to sham injection in patients with GA secondary to AMD as indicated by:
  - NEI VFQ-25 composite score
  - NEI VFQ-25 near activity subscale score (in select countries)
  - Comparison between study eye and fellow eye in change in GA lesion size
  - To evaluate the binocular maximum reading speed as assessed by MNREAD or Radner Reading Charts (in select countries)
  - To evaluate the binocular critical print size as assessed by MNREAD or Radner Reading Charts (in select countries)
  - To evaluate the relationship between genetic polymorphisms associated with AMD with GA progression and response to pegcetacoplan
- To evaluate the incidence of new onset of subclinical CNV in the study eye
- To assess sensitivity and specificity of a digital reading speed application to detect disease progression/regression (optional, select sites)
- To assess sensitivity and specificity of a digital visual function application to detect disease progression/regression (optional, select sites).

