### 6.1. Patient Selection

#### 6.1.1. Inclusion Criteria

The study eye must meet all inclusion criteria. If both eyes meet the inclusion criteria, the eye with the worst normal luminance visual acuity at the screening visit will be designated as the study eye. If both eyes have the same visual acuity, the right eye will be selected as the study eye.

Ocular-specific inclusion criteria apply to the **study eye** only, unless otherwise specified.

1. Age  $\geq 60$  years.
2. Normal luminance best corrected visual acuity of 24 letters or better using Early Treatment Diabetic Retinopathy Study (ETDRS) charts (approximately 20/320 Snellen equivalent).
3. Clinical diagnosis of GA of the macula secondary to AMD as determined by the investigator and confirmed by the reading center.
4. The GA lesion must meet the following criteria as determined by the central reading center's assessment of FAF imaging at screening:
  - a. Total GA area must be  $\geq 2.5$  and  $\leq 17.5$  mm^2 (1 and 7 disk areas respectively).
  - b. If GA is multifocal, at least 1 focal lesion must be  $\geq 1.25$  mm^2 (0.5 disk areas), with the overall aggregate area of GA as specified above in 4a.
  - c. The entire GA lesion must be completely visualized on the macula centered image and must be able to be imaged in its entirety and not contiguous with any areas of peripapillary atrophy.
  - d. Presence of any pattern of hyperautofluorescence in the junctional zone of GA. Absence of hyperautofluorescence (ie, pattern = none) is exclusionary.
5. Adequate clarity of ocular media, adequate pupillary dilation, and fixation to permit the collection of good quality images as determined by the investigator
6. Female subjects must be:
  - a. Women of non-childbearing potential, or
  - b. Women of childbearing potential (WOCBP) with a negative serum pregnancy test at screening and must agree to use protocol-defined methods of contraception for the duration of the study and refrain from breastfeeding for the duration of the study.
7. Males with female partners of childbearing potential must agree to use protocol-defined methods of contraception and agree to refrain from donating sperm for the duration of the study.

8. Willing and able to give informed consent and to comply with the study procedures and assessments.

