2.1.5. Exploratory Objectives

- To evaluate the efficacy of pegcetacoplan compared to sham in subjects with GA secondary to AMD as indicated by:
 - NEI VFQ-25 composite score
 - NEI VFQ-25 near activity subscale score (in select countries)
 - Comparison between study eye and fellow eye of change in GA lesion size
 - To evaluate the binocular reading speed as assessed by MNRead or Radner Reading Charts (in select countries)
 - To evaluate the binocular critical print size as assessed by MNRead or Radner Reading Charts (in select countries)
 - To evaluate the relationship between genetic polymorphisms associated with AMD with GA progression and response to pegcetacoplan
- To evaluate the incidence of new onset of subclinical CNV in the study eye.
- To assess sensitivity and specificity of a digital reading speed application to detect disease progression / regression (optional, select sites)
- To assess sensitivity and specificity of a digital visual function application to detect disease progression / regression (optional, select sites)

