2.2.4. Exploratory Endpoints

- Additional NEI-VFQ endpoints including:
 - Change from baseline in the NEI VFQ-39 distance activity subscale score (in select sites) over time.
 - Change from baseline in NEI VFQ-25 composite score over time.
 - Change from baseline in NEI VFQ-39 composite score over time.
 - Change from baseline in NEI VFQ-25 near activity subscale score (in select countries) over time.
 - Change from baseline in NEI VFQ-39 near activity subscale score (in select countries) over time.
 - Change from baseline in NEI VFQ-25 driving subscale score (in select countries) over time as well as the number and percentage of subjects with worse driving outcomes for subjects who are currently driving at baseline.
- Difference between study eye and fellow eye in change in GA lesion size from baseline over time in subjects with bilateral GA.
- Change from baseline in binocular maximum reading speed as assessed by MNRead or Radner Reading Charts (in select countries) over time.
- Change from baseline in binocular critical print size as assessed by MNRead or Radner Reading Charts (in select countries) over time.
- Change from baseline in digital reading index (in select sites) over time as measured by the Spotlight instrument.
- Change from baseline in digital visual function (metamorphopsia) (in select sites) over time as measured by the Alleye instrument.
- Progression from incomplete retinal pigment epithelium and outer retinal atrophy (iRORA) to complete retinal pigment epithelium and outer retinal atrophy (cRORA).
- Progression from large drusen to iRORA or cRORA.
- Other efficacy imaging endpoints including change in the distance of the atrophy junction to the fovea, and non-subfoveal atrophy to subfoveal atrophy conversion.

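### SAP 6.6.3 summarises each eye separately and does not produce the between-eye difference in GA change, its precision or its contrast with sham, although SAP 2.2.4 names that difference as an exploratory endpoint

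*SAP*

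**What the plan says.** The protocol (5.1.5) has the exploratory objective "Comparison between study eye and fellow eye in change in GA lesion size". The SAP (2.1.5) carries it over as "Comparison between study eye and fellow eye of change in GA lesion size", placed under the stem "To evaluate the efficacy of pegcetacoplan compared to sham in subjects with GA secondary to AMD as indicated by". SAP 2.2.4 then defines the endpoint as a quantity: "Difference between study eye and fellow eye in change in GA lesion size from baseline over time in subjects with bilateral GA".

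The analysis is in SAP 6.6.3. Its text begins "Descriptive summary statistics will be provided by treatment and visit for the change from baseline in total area of GA Lesion(s" and continues "for the study eye as well as for the fellow eye in subjects with bilateral GA with fellow eyes that satisfy the following characteristics". Four fellow-eye conditions follow: no CNV in the medical history, lesion size within the trial's entry range, hyperautofluorescence at the lesion margin, and no confluence with peripapillary atrophy. The only other output is a figure in which the change and its standard error "in the study eye as well as the fellow eye will be plotted over time by treatment group".

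Three other places bear on the point:

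- SAP 6.6 says that the exploratory endpoints listed in 2.2.4 will be evaluated.
- SAP 6 offers the primary MMRM as a fallback for continuous endpoints that have no stated model, but only where it is needed.
- SAP 15 lists departures from the protocol. It records that low luminance deficit will only be listed, and says nothing about the between-eye difference.

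**The concern.** The endpoint is a difference, but the analysis section describes its two components and stops there. The 6.6.3 output would contain no within-subject difference, no SE or CI for it, and no statement of how that difference in either active arm compares with sham.

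Both gaps matter for what this endpoint can offer. A fellow eye in the same patient is a natural control for patient-level drivers of lesion growth, and the gain comes from pairing. Two separate curves with separate error bars do not show that gain.

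The contrast with sham matters because the study eye is not picked at random. For a patient whose two eyes are each eligible, the rule in Protocol 6.1.1 is: "the eye with the worst normal luminance visual acuity at the screening visit will be designated as the study eye". The right eye is taken if acuity is equal. A gap between the eyes within one arm could therefore partly reflect how the eye was chosen. The same gap in sham is the reference that addresses this.

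**Working it through.** **Endpoint against analysis.** Neither document states a sample size, power or alpha for this endpoint, so there is no figure to reproduce. The check is whether each element implied by 2.1.5 and 2.2.4 is produced by 6.6.3.

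| Element | In 6.6.3? |
|---|---|
| Change in each eye, by arm and visit | Yes, sham included |
| Study-eye minus fellow-eye change per subject | Not specified |
| SE or CI of that difference | Not specified |
| PM or PEOM against sham for that difference | Not specified |
| Population as in 2.2.4 (bilateral GA) | Narrower: four added fellow-eye conditions |

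**What can be recovered.** If the same subjects supply both eyes at a visit, the mean of the paired differences equals the difference of the two eye means. The point estimate, and its contrast with sham, can then be read from the 6.6.3 tables. Section 6.6.3 does not require that both eyes be measured at the visit. The SE cannot be recovered, because it depends on the between-eye correlation ρ, which is not reported.

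**Illustration of the precision lost.** Inputs:

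- SD of lesion growth 1.50 mm² (SAP 3.4), assumed to hold in both eyes. As a check on this input, 200 per group, alpha 0.0495 and differences of 2.13 − 1.47 = 0.66 and 2.13 − 1.70 = 0.43 mm² give power of 99.3% and 81.7%. SAP Table 1 states 99.2% and 81.5%.
- ρ is not in the documents. Assumed 0.3, 0.5 and 0.7.
- Subjects with a qualifying fellow eye: not in the documents. Assumed 100 per group, half of 200.

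Formulas:

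- SD of the paired difference = 1.5 × √(2(1 − ρ)).
- SD implied by treating the eyes as independent = 1.5 × √2 = 2.12 mm².
- Overstatement of the SE = 1/√(1 − ρ) − 1.
- 95% half-width of an active-minus-sham contrast = 1.96 × SD × √(2/100).

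| ρ | SD of paired difference (mm²) | SE overstated by | Half-width, paired (mm²) | Half-width, as if independent (mm²) |
|---|---|---|---|---|
| 0.3 | 1.77 | 20% | 0.49 | 0.59 |
| 0.5 | 1.50 | 41% | 0.42 | 0.59 |
| 0.7 | 1.16 | 83% | 0.32 | 0.59 |

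**Visits available.** The SAP schedules (Appendix 1, Tables 8 to 11) take FAF in both eyes at Day 1 and at Months 6, 12, 18 and 24 on both regimens. The other post-baseline FAF visits are study eye only. The paired difference can be formed at those four visits without new data.

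**The case against.** The strongest reply is that this endpoint is exploratory and Protocol 12.7.3 promised only summary statistics for such endpoints. Other exploratory endpoints, such as the additional VFQ scores and binocular reading, are also only described by arm. Section 6.6.3 shows both eyes in every group, so sham sits beside the active arms. The difference is defined in 2.2.4, 6.6 says it will be evaluated, and the default MMRM in Section 6 could supply a comparison.

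Much of this stands. A reader might infer that the objective goes unanswered, or that the SAP nowhere contemplates the difference. The documents do not support that: the endpoint is defined, sham is displayed and an informal comparison is possible. What remains is that a mean difference with its SE is itself a summary statistic, and 6.6.3 does not provide it. The default model is discretionary, and 6.6.3 already prescribes a descriptive approach.

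Two other strong readings also fail:

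- **That the plotted standard errors are wrong.** They are correct for what they label, the mean change in each eye. The 20% to 83% describes an error that a reader could make by combining them, and with positive correlation that error is conservative.
- **That the study eye is always the worse-seeing one, so the curves are confounded throughout.** The rule applies only when both eyes meet the inclusion criteria. The 6.6.3 conditions omit some of these, including the 24-letter acuity limit and the 1.25 mm² focal-lesion rule. A fellow eye below 24 letters could enter the subset while the study eye sees better. SAP 5.2 records better-seeing or worse-seeing status for the study eye. Nor do the documents show that worse acuity goes with different GA growth.

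**Conclusion.** The concern holds as a mismatch between a named endpoint and its analysis section. SAP 2.2.4 asks for the between-eye difference, and 6.6.3 does not produce that difference, its precision or its contrast with sham. SAP 15 does not declare the omission. The populations in the two sections also differ.

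Severity is low. Efficacy rests on the randomised study-eye comparison in SAP 6.2, and nothing here affects alpha or the primary or key secondary conclusions. The estimate itself is largely recoverable. What is lost is its SE or CI. The size of that loss is illustrative only: it assumes a planning SD from the whole trial applied to both eyes of a selected subset, and a correlation that the documents do not give.

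**What to change.** In SAP 6.6.3:

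1. For each subject with both eyes measured, derive study-eye minus fellow-eye change from baseline at Months 6, 12, 18 and 24.
2. Summarise it by arm with 95% CIs.
3. Give nominal PM-minus-sham and PEOM-minus-sham contrasts with 95% CIs from an MMRM of the 6.2.2 type. That model cannot be used unchanged. Drop the fellow-eye CNV term, which is essentially constant here because the subset requires no CNV history in that eye, and enter the baseline lesion area of both eyes as covariates.
4. Keep the analysis exploratory, with no formal test.
5. State that a within-arm eye difference alone is not evidence of effect, because the study eye is not chosen at random: it is the worse-seeing eye when both eyes qualify, or the right eye if acuity is tied.
6. Align the population in 2.2.4 with the four fellow-eye conditions in 6.6.3.

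The cost is SAP wording, one derived variable and one adapted model on images already scheduled. There is no multiplicity cost.
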